8.1.5 Subject Follow-up

Make every attempt to follow the subject until the adverse event is resolved, stabilized, returned to baseline or deemed irreversible.

8.2 Special Situations

The Investigator must report all special situations **within 24 hours** by telephone or by fax using the form supplied by the Sponsor, to both the Drug Safety group and the Clinical Manager of the Sponsor as listed in Table D.

Special situations include but are not limited to the following: accidental overdose of IP, medication error with IP (such as administration of the wrong drug or wrong dose, wrong administration rate or wrong technique in drug usage process, administration via the wrong route, radiation under-dose, labeled drug-drug or drug-disease or drug-food interaction). In addition, any pregnancy of a subject or partner must be reported by the Investigator to the Sponsor within 24 hours using the Pregnancy Report form; any associated SAEs must be reported concurrently using the SAER.

In case urgent safety measures are taken during the conduct of the study these will be timely communicated by the Sponsor to the applicable regulatory authorities and also to concerned investigators and subjects.

8.3 Laboratory Evaluations

8.3.1 Reporting and Evaluation of Central Laboratory Test Results

The central laboratory will send a report of the laboratory results to the Investigator within 48 hours after the sample is picked up from the investigational site. Attach a copy of the laboratory report to the Case Report Form.

The Investigator or sub-investigator must review laboratory values within 24 hours of receipt of the laboratory report. After the review is completed, the Investigator must sign and date each laboratory report.

The central laboratory will provide normal reference ranges for the laboratory tests on the laboratory results report. A value is **normal** when it falls on or within the upper and lower limits of the reference range. A value is **abnormal** when it falls outside the upper or lower limit of the reference range. The central laboratory will flag all abnormal values on the laboratory report and will verify that the result is not due to pre-analytical problems (e.g., sample taken improperly, sample stored incorrectly, sample labeled incorrectly) or to analytical problems (e.g., machine not accurately calibrated, technical problems with equipment or reagents, deterioration of analyte).

The central laboratory has established 'alert criteria' for some laboratory tests and will make an **immediate telephone call** to the Investigator in the event that a laboratory result meets these criteria.

The Investigator must evaluate any change from pre dose to post dose in a laboratory test which represents a worsening of the subject's clinical state as to whether it meets the definition of an adverse event. **Record all changes determined to meet the definition of an adverse event in the Adverse Event section of the Case Report Form.**

8.3.2 Repeat Testing

Collect additional samples to repeat the lab test that represents a worsening of the subject's clinical state and meets the definition of an adverse event, until the value returns to the pre dose level or clinically stabilizes, or until the Investigator or physician of record determines that further follow-up is unnecessary.

8.3.3 Emergency Laboratory Analysis

If a laboratory result needs to be obtained immediately, split the sample and send one-half to the local laboratory for immediate analysis and the other half to the central laboratory. Attach results from both laboratories to the Case Report Form.

8.4 Electrocardiograms

If a worsening from pre dose to post dose is observed on an ECG, repeat the ECG at the discretion of the Investigator, in addition to obtaining an ECG at the 30 min and 24 hours post dose time points required by the protocol. The Investigator will assess any worsening from pre dose to post dose in the ECG for clinical relevance (whether it meets the definition of an adverse event). Record all changes determined to meet the definition of an adverse event in the Adverse Event section of the Case Report Form.

8.5 Physical Examinations

If a worsening from pre dose to post dose is observed, repeat the physical examination at the discretion of the Investigator, in addition to obtaining a physical examination at the 24 hour post dose time point required by the protocol. The Investigator will evaluate any worsening at the post dose physical examination for their clinical relevance and to determine whether they meet the definition of an adverse event. Record all changes determined to meet the definition of an adverse event in the Adverse Event section of the Case Report Form. Record specific signs, symptoms, and/or laboratory information supporting these changes.

8.6 Vital Signs

If a worsening from pre dose to post dose is observed in vital signs, repeat the vital sign measurement at the discretion of the Investigator, in addition to obtaining vital sign measurements at 5 minutes, 30 minutes and the 24 hour post dose time points as required by the protocol. The Investigator will evaluate any worsening in vital signs for its clinical relevance as to whether it meets the definition of an adverse event. Record all changes determined to meet the definition of an adverse event in the Adverse Event section of the Case Report Form.

9 Statistical Methods

In general, summary statistics (mean, median, standard deviation, minimum, and maximum) will be provided for continuous variables, and the number and percentage of each category will be provided for categorical data. Any changes in the original statistical methodology will be documented in the statistical analysis plan (SAP).

All statistical analyses will be performed using SAS® software.

9.1 Subject Disposition and Demographic and Baseline Characteristics

Summary tables will be provided for the number of subjects who have been enrolled, dosed and completed according to the protocol. The number of subjects who prematurely discontinued the study and the reasons for their discontinuation will be summarized.

Summary statistics will be presented for demographic and baseline characteristics, including age, sex, race, height, and weight, BMI, other relevant study entry criteria.

9.2 Analysis Population

Safety Analysis Population – all subjects who received IP will be included in the safety analysis population.

Efficacy Analysis Population – all subjects who received IP and have data available for both non-contrast echo exam and contrast echo exam will be included in modified Intent-to-Diagnose population (ITD population).

9.3 Concomitant Medications

Frequencies of concomitant medication use will be tabulated by World Health Organization (WHO) class, level I and level II.

9.4 Extent of Exposure

Descriptive statistics will be presented to summarize the volume (mL) of IP administered. Dose administration for IP will be listed for each injection by subject.

9.5 Safety Analysis

The safety data will be summarized for all subjects dosed. Summary tables, including change from UEUS to CEUS or clinically significant changes where applicable, will be presented for the following safety endpoints:

- Adverse Events
- Clinical Laboratory Evaluations
- Electrocardiograms
- Pulse Oximetry
- Vital Signs

All adverse events will be coded by MedDRA and summarized by system organ class and preferred term, by intensity and by causal relationship to the investigational product.

Only those occurrences which occur from the start of IP administration through the follow-up period defined in the protocol will be tabulated in the Clinical Trial Report as “adverse events” See Section 8.1.1.

Physical examination results, concomitant medication data will be presented in the data listings.

Summary statistics will be presented for volume of investigational product administered.

9.6 Pharmacokinetics Analysis

Pharmacokinetic parameters will be calculated from blood data. The actual times (i.e., not the nominal sampling times) at which blood samples obtained will be used in all calculations. Blood concentrations below the limits of quantification will be replaced with zero for the calculation of all pharmacokinetic parameters. The blood concentration-time data will be analyzed using appropriate software.

A listing of all raw blood concentration data and tables containing standard descriptive statistics will be reported. Profiles of blood concentrations will be represented graphically for the mean and individual data to show the inter-subject variability. The pharmacokinetic parameters will be normalized by subject body weight if applicable. Appropriate pharmacokinetic compartment/non-compartment modeling will be applied based on the performance of goodness of fit criteria and the inter-subject variability of the subject pharmacokinetic profiles. Pharmacokinetic analysis approach will be similar to the methodology utilized in the adult study [REDACTED] to be able to compare the results between pediatric and adult pharmacokinetic data.

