Most or all of contrast agent dose rapidly dissolves in the blood and subsequently eliminates by the lungs. The cumulative recovery of SF₆ in expired air averaged 86% to 94% of the administered dose in healthy subjects.³³ The results of this study published by Morel et al³⁶ had shown that LUMASON rapidly removed from the blood by the pulmonary route with 40% to 50% of the injected dose eliminated within the first minute after administration and 80% to 90% eliminated by 11 minutes after administration. Furthermore, the recovery of SF₆ in expired air in subjects with impaired lungs averaged 102%.³⁴ This finding indicates that the patients eliminate all of the SF₆ from LUMASON via their lungs rather than an alternate elimination route, despite the impairment of lung function. Most alveolar maturation occurs in the first 2 years of life, so that no differences in the elimination of the gas between adults and pediatric patients 9-17 years-old should be expected.³⁵ No studies ever reported the use of ultrasound contrast agents during rest echocardiography in patients below 9 years of age.

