7.6 Pharmacokinetic Evaluation

A subset of subjects at one or two sites will undergo additional blood sampling for the determination of SF₆ concentration in blood. A total of 6 subjects (3 males and 3 females) age 9 and up to 12 years of age, and 6 subjects (3 males and 3 females) in the age >12 and up to and

[figure not shown]
including 17 years will have additional blood draws of 1 mL each immediately pre-dose, and at 1, 2, 3, 5, 10 and 15 minutes post-dose for the purposes of analyzing SF₆ concentration in blood. Blood samples will be taken from the arm contralateral to that used for the injection of LUMASON and analyzed by gas chromatography-mass spectrometry (GC-MS) or other acceptable method to obtain SF₆ concentration in blood. A designated laboratory will perform evaluations of SF₆.

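### Zero substitution for all below-quantification SF6 values does not separate the pre-dose sample from late post-dose samples; if late zeros enter an untransformed compartmental fit, the terminal half-life is biased short

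*Combined protocol and SAP*

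**What the plan says.** Section 9.6 gives one rule for values below quantification, with no exception by sampling time: "Blood concentrations below the limits of quantification will be replaced with zero for the calculation of all pharmacokinetic parameters". It leaves the estimation method open: "Appropriate pharmacokinetic compartment/non-compartment modeling will be applied based on the performance of goodness of fit criteria". It gives no weighting, error model or terminal-slope rule, and does not name terminal half-life as a planned parameter. It also says "Pharmacokinetic analysis approach will be similar to the methodology utilized in the adult study", a study whose reference is redacted, so as "to be able to compare the results between pediatric and adult pharmacokinetic data".

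Section 7.6 schedules blood draws "immediately pre-dose, and at 1, 2, 3, 5, 10 and 15 minutes post-dose", to be "analyzed by gas chromatography-mass spectrometry (GC-MS) or other acceptable method". No quantification limit is given. Section 5.2 reports, from adult work, 40-50% of the dose eliminated in the first minute and "80% to 90% eliminated by 11 minutes after administration". Sections 5.1, 7.6 and 9.8 set the subset at 12 subjects.

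**The concern.** Before dosing, zero is the natural value. After dosing, a result below the limit means a concentration somewhere between zero and the limit, and zero understates it. Only two of the six post-dose samples come after 5 minutes, and both fall around or after the time by which, on the protocol's own account, most of the gas has gone. If any samples are below the limit, these are the likely ones, and they carry most of the information on the terminal phase.

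Zeros can enter in two ways. In a compartmental model fitted to untransformed concentrations they act as data and pull the tail of the curve down, which shortens the fitted half-life. In a linear-trapezoid AUC they remove area, so any clearance derived from that AUC rises. Both errors point towards faster elimination. Section 9.6 wants results that can be set beside adult data, and Section 5.2 expects no difference in gas elimination between adults and children aged 9-17, so an effect of the assay limit could be mistaken for physiology. The error is systematic, so averaging over 12 subjects would not remove it.

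**Working it through.** The plan states no half-life, quantification limit or expected count of low values, so there is no pharmacokinetic figure to reproduce. What follows is an illustration.

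**Inputs from the protocol.** Post-dose samples at 1, 2, 3, 5, 10 and 15 minutes (7.6); 40-50% of the dose eliminated by 1 minute and 80-90% by 11 minutes (5.2).

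**Assumptions.** Fraction of dose remaining R(t) = f·exp(-at) + (1-f)·exp(-bt), with b = ln 2 / terminal half-life; half-life 6, 8, 10 or 12 minutes; no noise; unweighted biexponential least squares. Section 5.2 gives dose fractions, not blood levels, so two links were used:

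- Link 1: blood level proportional to R(t).
- Link 2: elimination rate proportional to blood level, so blood level is proportional to f·a·exp(-at) + (1-f)·b·exp(-bt).

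**Worked example (link 1).** Take 55% remaining at 1 minute, 15% at 11 minutes, half-life 8 minutes.

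- b = 0.693/8 = 0.0866. The fast term is negligible by 11 minutes, so 1-f = 0.15·exp(11 × 0.0866) = 0.389 and f = 0.611.
- a = -ln[(0.55 - 0.389·exp(-0.0866))/0.611] = 1.151.
- Levels at the six times, as % of dose: 55.0, 38.8, 31.9, 25.4, 16.4, 10.6.
- 15-minute sample set to zero: fitted half-life 4.76, and 4.76/8 = 60% of true.
- 10- and 15-minute samples set to zero: fitted half-life 2.90, and 2.90/8 = 36% of true.
- Those samples dropped instead: 8.0 in both cases. With two dropped this is four parameters on four points, so it shows absence of bias, not precision.
- AUC(1-15): 46.9 + 35.4 + 57.3 + 104.5 + 67.5, about 311.5. It becomes 285.0 with one zero (8.5% lower) and 203.2 with two (35% lower).
- Log-linear slope on the last three quantifiable points: half-life 7.93 with none lost, 7.36 with one lost, 5.05 with two lost. A zero has no logarithm, so these are the same whether the lost samples are coded zero or missing. The shortening comes from losing late samples, not from the zeros.

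**Over the protocol's range.** Elimination pairs 40/80%, 45/85% and 50/90%, half-lives 6-12 minutes (6 is not attainable with 40/80%):

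| | Link 1 | Link 2 |
|---|---|---|
| 15-min level, % of 1-min level | 13-27 | 1.5-6 |
| Half-life, % of true, one zero | 40.0-76.4 | 36.7-70.6 |
| Half-life, % of true, two zeros | 19.9-52.9 | 12.7-40.5 |
| AUC(1-15) loss %, one zero | 6.5-10.6 | 2.5-6.3 |
| AUC(1-15) loss %, two zeros | 29.9-39.0 | 9.2-25.8 |

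Together: half-life about 37-76% of true with one zero and 13-53% with two; AUC about 2-11% and 9-39% lower. These are not bounds. Crossing 40, 45 and 50% with 80, 85 and 90% in every feasible combination widens the half-life ranges to 30-79% and 11-57%, and the AUC losses to 2-11% and 8-41%.

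**Alternatives to zero, with noise.** In a simulation of 150 subjects per setting (link 2, half-life 6 or 8 minutes, 15% proportional error, limits up to 8% of the 1-minute level), omitting the low values gave fitted half-lives of 103-120% of true; treating them as left-censored gave 70-89%.

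**The case against.** The strongest objection is that every step is conditional. A reader might infer that the rule simply makes the paediatric half-life too short. The documents do not support that: no quantification limit is stated, so no late sample is shown to be below it; 9.6 equally allows non-compartmental analysis, where a log-linear slope drops zeros; and half-life is not a named parameter. This stands, and the point is worded accordingly.

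A reader might also tie the bias to a particular limit, say 5% of the 1-minute level. That does not stand either. Under link 1 the 15-minute level is 13-27% of the 1-minute level, and such a limit would catch no expected value; under link 2 it is 1.5-6%, and it often would. The protocol does not settle which link applies.

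A third inference is that children would wrongly appear to clear the gas faster than adults. That assumes the adult data were not handled in the same way. The adult reference is redacted, so its rule and limit cannot be checked. If adults were analysed with zeros, part of the bias may be shared, and changing only the paediatric rule would itself create a difference.

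Finally, pharmacokinetics is a secondary objective with no test or success criterion. Section 9.6 commits to listing raw concentrations, plotting individual profiles and choosing models by goodness of fit, and Section 9.9 leaves data-handling detail to the SAP. These would make zeroed points visible. They do not alter the stated rule, which covers all parameters.

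**Conclusion.** The point holds conditionally. Section 9.6 states a rule rather than leaving a gap, and the rule treats the pre-dose and terminal samples alike. If late samples are below the limit and the zeros enter an untransformed compartmental fit, the half-life is biased short. The direction was the same in every setting tried; the sizes rest on the assumed biexponential shape, half-lives of 6-12 minutes, the blood-level link and unweighted fitting. AUC by the linear trapezoid is lowered under the same first condition, so non-compartmental work is not wholly exempt even though its log-linear half-life is. There is no effect if all post-dose samples are quantifiable. This is an inexpensive improvement to a secondary analysis and does not touch the efficacy conclusions.

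**What to change.** In Section 9.6, and in the matching SAP text:

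- Use zero only for the pre-dose sample.
- Exclude post-dose values below quantification from the terminal slope, and treat them as missing in non-compartmental analysis and in individual compartmental fits. State AUC as running to the last quantifiable time, with any extrapolated part shown separately.
- Offer a left-censored likelihood as an alternative or sensitivity analysis. It is not proposed as the main method because omission came closer to the true half-life in the simulation above, and six post-dose points per subject give a censored biexponential little to work with.
- Report the quantification limit and the number of post-dose values below it, by sampling time.
- If the adult study used zero substitution, add a labelled zero-substitution sensitivity analysis for the paediatric-adult comparison.

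The cost is a short rewording and slightly more programming. The drawback is that the main values may follow a different rule from the adult report; the sensitivity analysis covers this.

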9.7 Efficacy Analysis

The primary analysis will be based on the off-site reader evaluations. The analysis will be performed and presented separately for each reader. There will be no adjustment for multiple readers. There will be 2 primary endpoints for the study: the change from baseline (UEUS to CEUS) in total LV EBD score and proportion of subjects with adequate LV opacification. As we have to achieve success for both endpoints there will be no multiplicity adjustment for the analysis and power consideration.

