9.7.2 Analysis Methods

9.7.2.1 Analysis of LV EBD Score

The null hypothesis of the primary test is that there is no difference between the CEUS and UEUS in the mean total LV EBD score in the pediatric population. The alternative hypothesis is that the CEUS is superior to UEUS in term of the mean total LV EBD score in pediatric population.

$H_0: \mu_{CE} - \mu_{UE} = 0$

$H_1: \mu_{CE} - \mu_{UE} > 0$

where μ_{UE} represents the mean of the total LV EBD score for the UEUS; and μ_{CE} represents the mean of the total LV EBD score for the CEUS.

For each blinded reader assessment, paired t-test will be used to compare total LV EBD score between the CEUS and UEUS. In addition, the 2-sided 95% confidence intervals (CIs) will be calculated for the mean total LV EBD scores for each exam as well as for the change from baseline (UEUS to CEUS). The distribution of the individual scores (0, 1, or 2) assigned to each of the 17 ventricle segments will be presented.

The study will be considered as a success for the primary efficacy endpoint if: 2 of the 3 readers achieve superiority of the CEUS over the UEUS in terms of the mean total LV EBD score. The satisfaction of superiority is met if the alternative hypothesis is concluded, i.e., $\mu_{CE} - \mu_{UE} > 0$ based on paired t-test at significance level of 0.05.

Inter-reader agreement of the assessment for each segment among 3 off-site readers will be evaluated (for UEUS and CEUS separately) by kappa statistic.

The number and percentage of subjects with reduction of inadequate LV EBD in at least one pair of adjacent segments (combined 4-chamber, 2-chamber, and 3-chamber view) following administration of IP will be summarized for each reader.

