9.7.2.2 Analysis of LV Opacification

The proportion and its 95% CI of subjects with adequate LV opacification scores at the CEUS will be estimated using binomial proportion estimate method. Assuming expected proportion of subjects with adequate LV opacification scores at the CEUS is 80%. The success criteria for the LV opacification score will be 2 out of 3 blinded readers reach >70% as the lower limit of 95% confidence limit for the proportion of subjects with adequate LV opacification score.

Inter-reader agreement of the assessment of adequate LV opacification for each subject among 3 off-site readers will be evaluated by kappa statistic.

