9.8 Sample Size

Sample size determination for this study was based on the 2-tailed paired t-test using software nQuery Advisor 7.0. The primary objective of this trial is to show a significant intra-subject change in total of LV EBD scores for each subject (Hypothesis specified above) from UEUS to LUMASON -enhanced echocardiography. Sample size determination for this study was based on the 2-tailed paired t-test.

A peer-reviewed publication showed ³⁷ that the percentage of endocardial border visualization at unenhanced harmonic images (74%) was significantly lower comparing to a contrast enhanced images (88%) in the suboptimal subjects non-diagnostic imaging group, which translated to the difference of 4 in total LV EBD scores. A previously conducted Bracco-sponsored study [REDACTED] had the same endpoint of the total LV EBD score range 0-32 assessed on harmonic

images on adult subjects with known or suspected coronary artery disease. The results from the analysis of the suboptimal subjects in this study showed that the average difference of the total LV EBD score between CEUS and UEUS was 3.2; the standard deviation of the difference was 8.3. Based on these results as the assumptions for current study and considering the probability of a Type I error (α) of 0.05 and the probability of a Type II error (β) of 0.10, 73 subjects will be needed to show a difference between CEUS and UEUS for 90% of power.

When the sample size is 73, a 2-sided 95% CI for a single proportion using the large sample normal approximation will extend 9% from the observed proportion for an expected proportion of 80% subjects with adequate LV opacification score. This can be translated as lower limit of 95% CI >70% for the observed proportion of subjects with adequate LV opacification score.

Based on the above considerations, for both endpoints (Total LV EBD score and LV opacification score), total of 73 evaluable subjects are needed. Considering 20% of early dropout, 92 subjects will need to be enrolled.

A subset of 12 subjects is considered to be sufficient for the estimation of the pharmacokinetic parameters, based on the findings of a prior study in healthy subjects.

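### The only stated power (90%) is for one reader on the EBD score; the chance of meeting both co-primary endpoints is not stated and is about 0.55 to 0.66 on the plan's own inputs

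*Combined protocol and SAP*

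**What the plan says.** Section 9.7 names two primary endpoints, the change in total LV EBD score and the proportion of subjects with adequate LV opacification, and requires success on both. It continues: "As we have to achieve success for both endpoints there will be no multiplicity adjustment for the analysis and power consideration".

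Each endpoint has its own reader rule. For the EBD score (9.7.2.1), success means that "2 of the 3 readers achieve superiority of the CEUS over the UEUS in terms of the mean total LV EBD score". For opacification (9.7.2.2), it means that "2 out of 3 blinded readers reach >70% as the lower limit of 95% confidence limit", with an expected proportion of 80%.

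Section 9.8 sets the sample size. It states that "Sample size determination for this study was based on the 2-tailed paired t-test", takes a mean difference and SD from an adult study ("CEUS and UEUS was 3.2; the standard deviation of the difference was 8.3"), and concludes that "73 subjects will be needed to show a difference between CEUS and UEUS for 90% of power". For opacification it gives no power. It notes that at n = 73 a normal-approximation 95% interval extends 9% either side of an observed 80%, so that the lower limit is above 70%. It then takes 73 evaluable subjects as the number for both endpoints.

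**The concern.** A both-must-succeed rule protects the type I error, so neither test needs a smaller alpha. For power it works the other way: the probability of passing both tests cannot exceed the smaller of the two separate probabilities and is usually below both. If the 9.7 sentence is meant to excuse the plan from considering joint power, the reason it gives points in the wrong direction.

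Whatever the sentence means, the plan gives one power figure, for one reader on one endpoint, and then applies the resulting sample size to a rule with two endpoints and a 2-of-3-reader requirement on each. No figure describes the rule that decides the trial. At stake is how the sponsor, ethics boards and later readers judge the chance that 73 evaluable children will give a conclusive result. Type I error across the two endpoints is not affected.

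**Working it through.** **Inputs.** From 9.8: mean difference 3.2, SD of the difference 8.3, two-sided alpha 0.05, n = 73, normal-approximation interval. From 9.7.2.2: expected opacification proportion 0.80 and a lower 95% limit that must exceed 0.70. The documents give no correlation between readers or between endpoints, so these are assumed and varied.

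**Step 1: the plan's own figures.** The paired t-test has noncentrality (3.2/8.3) × √73 = 3.294 on 72 degrees of freedom, with critical value 1.993. Power from the noncentral t distribution is 0.901, and 73 is the smallest n that reaches 0.90. The interval half-width is 1.96 × √(0.80 × 0.20/73) = 0.092, giving a lower limit of 0.708, which agrees with the stated 9%. Enrolment is 73/0.80 = 91.25, rounded up to 92. All three reproduce.

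**Step 2: power for opacification, one reader.** Find the smallest count whose lower limit exceeds 0.70, then the binomial probability of reaching it at a true 0.80.

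| Interval method | Count needed of 73 | Probability at 0.80 |
|---|---|---|
| Normal approximation (named in 9.8) | 58 (79.5%) | 0.614 |
| Wilson | 59 (80.8%) | 0.500 |
| Exact (Clopper-Pearson) | 60 (82.2%) | 0.384 |

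The required count lies almost at the expected value, so the chance of reaching it is not far from one half. A precision statement about an observed 80% does not show this.

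**Step 3: both endpoints, one reader.** With independent endpoints and the normal approximation, 0.901 × 0.614 = 0.554. Without any assumption on dependence, the bounds are 0.901 + 0.614 − 1 = 0.516 (from unrounded values) and 0.614. With jointly normal test statistics, correlation 0.5 gives 0.59 and 0.8 gives 0.61. With exact limits and independence, 0.901 × 0.384 = 0.346.

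**Step 4: the 2-of-3-reader rule.** If readers are independent, the chance that at least two pass is 3p²(1 − p) + p³. This gives 0.973 for EBD and 0.668 for opacification, so 0.973 × 0.668 = 0.650 jointly. If readers agree perfectly, the result returns to the single-reader 0.554. Simulation over reader correlations from 0 to 0.999 and endpoint correlations of 0 and 0.5 gave about 0.55 to 0.66 with the normal approximation and about 0.31 to 0.36 with exact limits.

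**Step 5: sensitivity.** Testing EBD one-sided at 0.05 raises its power to 0.947 and the single-reader joint figure to 0.947 × 0.614 = 0.582. If the true opacification rate is 85% or 90%, opacification power is 0.927 or 0.998, and the single-reader joint figure about 0.84 or 0.90.

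**Step 6: what the joint requirement contributes alone.** Two tests each with 90% power give 0.90 × 0.90 = 0.81 jointly if independent, with bounds of 0.80 and 0.90. On the plan's inputs the fall from 0.901 to 0.554 is 0.347, of which 0.901 − 0.614 = 0.287 is already present in opacification taken alone.

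**The case against.** Four objections have force.

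- The subject of the 9.7 sentence is multiplicity adjustment. A natural reading is that alpha is split neither in the tests nor in the power calculation, which is correct and is what 9.8 does by using the full 0.05. A reader might infer that the plan demonstrably misstates how power behaves. The wording does not establish that; it is ambiguous.
- A reader might also infer that the plan claims a 90% chance of overall success. It does not: 9.8 ties 90% to the EBD difference and supports opacification separately by interval width. Still, 90% is the only power given, and 73 is then adopted for both endpoints.
- Most of the shortfall comes from the sizing of opacification. This stands. The 55% to 66% should not be attributed to the both-must-succeed rule, nor counted a second time if the opacification sizing is raised separately.
- Independence is the less favourable assumption. Section 5.2 describes EBD improvement as resulting from opacification, so positive dependence is plausible, and the 2-of-3 rule raises EBD power. Section 9.7.2.1 also states a one-directional alternative at 0.05 without giving the sidedness of the test. These points move the normal-approximation figure within roughly 0.55 to 0.66; none brings it near 0.90. A true opacification rate of about 90% would do so, but the plan assumes 80%.

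**Conclusion.** The point holds as one about an unstated joint power and an ambiguous sentence. The no-adjustment statement is right for alpha and would be wrong if taken to cover joint power. The 90% is correct for one reader on EBD, but it does not describe the success rule, and 73 evaluable subjects do not deliver 90% for that rule at the plan's own inputs. With the normal-approximation interval, a true rate of 80% and two-sided EBD testing, the joint chance is about 0.55 (independent endpoints) to 0.61 (strongly correlated) for one reader, and about 0.55 to 0.66 under the 2-of-3 rule. The result depends on the interval method, which 9.7.2.2 does not fix, and on correlations that the documents do not give. The documents support neither a finding that alpha control fails across the endpoints nor one that the plan promised 90% for the trial as a whole.

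**What to change.** In 9.7, limit the sentence to alpha: because both endpoints must be met, no alpha adjustment across them is made.

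In 9.8:
- Label the 90% as *per reader, EBD endpoint alone*.
- State the power for opacification at n = 73 and a true rate of 80%.
- State the probability of meeting both endpoints in at least 2 of 3 readers, as a range over stated reader and endpoint correlations.
- Name the interval method for the proportion and the sidedness of the EBD test, and use the same choices in 9.7.2.1 and 9.7.2.2.

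The cost is a few lines of text and a short simulation. No test, success rule or enrolment figure changes. The drawback for the sponsor is a less favourable stated power.
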